7.6 Procedures for Discontinuation of Individual Research Subjects

The principal investigator or investigator shall terminate a research subject's research participation when the research subject meets the criteria described in Section 7.5. Individual research subjects may discontinue their research participation without giving a reason at any time during the research. Should a research subject's participation be discontinued, the primary reason for termination shall be recorded on the CRF by the

principal investigator or investigator. In addition, efforts shall be made to perform all tests/observations/evaluations scheduled at the time of discontinuation.

8.0 TREATMENT

8.1 Study Drug

8.1.1 Study drug

Nonproprietary name: Ramelteon [JAN]

Chemical name: N-{2-[(8S)-1,6,7,8-Tetrahydro-2H-indeno[5,4-b]furan-8-yl]ethyl}
propanamide

Dosage: 8 mg once daily

Method of administration: Orally at bedtime

Duration of treatment: 8 weeks

8.1.2 Overdose

Overdose is defined as intentional or accidental administration of the study drug at a higher dose than that specified in the protocol, either by a health professional or by the research subject.

To consistently collect important safety information about overdose, the principal investigator or investigator(s) shall record all cases of overdose on the "Overdose" page of the CRF, irrespective of the presence or absence of accompanying adverse event. Adverse events associated with overdose shall be recorded on the "Adverse events" page of the CRF, in accordance with the procedures described in Section 10.0, "ADVERSE EVENTS."

In addition, serious adverse events associated with overdose shall be recorded in accordance with the procedures described in Section 10.2.2, "Collection and reporting of SAEs."

In the event of overdose, the principal investigator or investigator shall treat the subject as required based on symptoms

8.2 Prescription of the Study Drug

The principal investigator or investigator will prescribe the study drug according to the protocol, to participants who fulfill all of the inclusion criteria and do not meet any of the exclusion criteria.

8.3 Prescription of Antidepressant Medication

The oral antidepressant medication being used in each participant at the time of 4 weeks prior to start of the run-in period will be continued without any change to the dosage regimen during participation in the study. Addition of antidepressant will not allowed after the time of 4 weeks prior to start of the run-in period.

8.4 Non-pharmacological Insomnia Treatment

During the study period, non-pharmacological insomnia treatment should be added or changed.

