6.0 STUDY DESIGN

6.1 Study Design

(1) Study design

This is a multicenter, open-label study.

(2) Treatment

Participants will take ramelteon 8 mg once daily orally at bedtime for 8 weeks.

(3) Planned sample size

30 patients

(4) Number of study sites

Approximately 5 medical institutions

(5) Duration of evaluation and number of visits in individual participants

The duration of evaluation in this study will be 9 weeks. Participants will make a total 4 visits, i.e., at the start of the run-in period and at the start and Weeks 4 and 8 of the treatment period.

Figure 6.a shows the schematic diagram of the study design. The study schedule is provided in Appendix A.

[figure not shown]

Figure 6.a Schematic of Study Design

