6.2 Rationale for the Study Design

<Rationale for the study population>

For ramelteon, a drug approved for "improvement of sleep onset difficulty in insomnia", data have been limited on its efficacy and safety in insomnia patients with psychiatric disease, and construction of the clinical evidence is desired. Among psychiatric diseases, depression is common and often coexists with insomnia symptoms. Thus, the study population is set to insomnia patients with depression.

<Rationale for the study design>

An uncontrolled, open-label design is employed in light of feasibility of this post-marketing clinical research, although the primary objective is to explore the effect of ramelteon in treating insomnia patients with a history of co-morbid depression.

<Rationale for the dosage>

The approved dosage and method of administration for ramelteon are employed.

<Rationale for the endpoints>

The "Guideline for Clinical Evaluation of Hypnotic Agents" (Notification No. 1213-1 of the Evaluation and Licensing Division, Pharmaceutical and Food Safety Bureau, dated December 13, 2011) recommends the use of polysomnography for objective efficacy evaluation in addition to the use of patient-recorded sleep logs for subjective efficacy evaluation. While polysomnography is a complex examination and repeated polysomnography can impose heavy burden on participants, actigraphy has been recognized to provide sleep data highly correlated with those provided by polysomnography and is a simple tool posing less burden to participants. Thus, actigraphy is selected as an objective assessment tool in this study¹⁰⁾. For subjective measures, this study uses a sleep diary, as well as the Patient Global Impression (PGI) as an index of global improvement, and the 3 Dimensional Sleep Scale (3DSS) as a new tool to assess sleep dimensions including sleep phases. The HAM-D17 is selected for evaluation of depressive symptoms, in line with preceding studies.

The safety will be evaluated based on adverse events, body weight.

<Rationale for the treatment duration>

The treatment duration is set to 8 weeks on the basis of the Japanese long-term clinical trial of ramelteon (24-week treatment), which demonstrated gradual

manifestation of the efficacy of ramelteon on sleep latency under repeated dosing over a certain period, and the efficacy peaked around Week 8.

<Rationale for the sample size>

See Section 13.3

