7.3 Prohibited Medications and Therapies

During the study period, the principal investigator or investigator will instruct the participants not to take any other medications than those instructed to be taken, including over-the-counter drugs, without first consulting with the principal investigator or investigator.

[Prohibited medications]

Fluvoxamine maleate will be prohibited from the start of the run-in period. Insomnia medications other than ramelteon (including investigational drug and unapproved drugs) will be prohibited from at least 2 weeks before treatment period to the end of the study period.

1. Fluvoxamine maleate
2. Insomnia medications other than ramelteon (including investigational drug and unapproved drugs)
3. Antidepressant medications other than those used at the time of 4 weeks prior to start of the run-in period

[Rationale for prohibited medications]

1. Fluvoxamine maleate is contraindicated for use with the study drug, ramelteon.
- 2, 3. Medications may prevent appropriate evaluation of the efficacy and safety of the study drug.

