7.5 Criteria for Discontinuation or Withdrawal of a Research Subject

The principal investigator or investigator shall record the main reason for discontinuation of protocol treatment on the case report form according to the classification described below. Refer to Section 9.1.12 for research subjects who withdraw from the research before

1. Adverse event

This is selected when an adverse event occurred in a study participant that requires premature termination to avoid an unacceptable risk to the participant's health imposed by continued participation in the study; or the study participant is unwilling to remain in the study because of the adverse event.

2. Major protocol deviation

This is selected when the study participant is found not to fulfill the protocol-specified eligibility criteria after the start of the study treatment, or has failed to adhere to protocol requirements, and thus the participant's continued participation in the study would pose an acceptable risk to his/her health.

3. Lost to follow-up

This is selected when the study participant has not returned to the study site and lost contact. In such instances, all attempts to contact the participant must be recorded in the source document.

4. Voluntary withdrawal

This is selected when the study participant has requested to withdraw his/her participation in the study. The reason for withdrawal, if provided by the participant, will be recorded in the case report form.

5. Discontinuation of the entire study

This is selected when discontinuation of the entire study is decided by the sponsor, institutional review board, regulatory authority, etc. See Section 6.3.1 for details.

6. Pregnancy

This is selected when a female study participant is found to be pregnant.

Note: A participant found to be pregnant must be immediately withdrawn from the study. For the withdrawal procedure, see Section 9.1.11.

7. Lack of efficacy

This is selected when the investigator or subinvestigator has judged that, because of lack of efficacy of study treatment, the participant's continued participation in the study would pose an unacceptable risk to the participant.

8. Sign of suicide

This is selected when the HAM-D17 "11: Suicide" item score became ≥ 1 ; or the principal investigator or investigator judged that the C-SSRS results or other findings indicate a sign of suicide.

9. Remission of depression

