9.1.3 History of insomnia

Regarding current insomnia, the following data will be obtained:

- Date of onset
- Initial/Recurrence
- Any non-pharmacological therapy

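### Protocol 8.4 tells sites that non-drug insomnia treatment should be added or changed; a 'not' has very probably been dropped, and no other rule covers such treatment on study

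*Protocol*

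**What the plan says.** Protocol 8.4 is a single sentence: "During the study period, non-pharmacological insomnia treatment should be added or changed". It stands identically in both protocol texts in the file.

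The neighbouring rules run the other way. Under 8.3, a participant's antidepressant "will be continued without any change to the dosage regimen during participation in the study". One of the two texts adds: "Addition of antidepressant will not allowed after the time of 4 weeks prior to start of the run-in period". Section 7.3 prohibits insomnia drugs other than ramelteon, on the ground that they may interfere with evaluating the study drug. Its heading is "Prohibited Medications and Therapies", but every item listed is a drug.

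The treatment plan in 6.1 is ramelteon alone: "Participants will take ramelteon 8 mg once daily orally at bedtime for 8 weeks". Non-drug treatment of insomnia otherwise appears only as history. Protocol 9.1.3 records "Any non-pharmacological therapy" for the current insomnia, and SAP 6.2.1 tabulates it as a baseline yes/no item.

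On design, Protocol 6.2 states: "An uncontrolled, open-label design is employed in light of feasibility of this post-marketing clinical research". SAP 7.1.1 tests the within-subject change in actigraphy sleep latency with a one-sample t-test. SAP 10.1 rules out covariate adjustment.

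**The concern.** Taken at its word, 8.4 directs or at least permits sites to start or alter a second treatment for the symptom that the primary endpoint measures. In a controlled trial, such a co-intervention might be expected to occur in both arms. Here there is no second arm, so its whole effect enters the mean change and the test credits it to the treatment period.

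The rule also matters in practice. No entry criterion excludes patients already using a non-drug insomnia therapy, and 9.1.3 anticipates that some will be. If the intended rule is to hold such therapy constant, the text as written does not state it, and a site that adds one commits no deviation.

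**Working it through.** **Is a 'not' missing?** The passages compare as follows.

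| Place | Rule or wording | Direction |
|---|---|---|
| Protocol 7.3 | Other insomnia drugs prohibited from at least 2 weeks before treatment to end of study | Hold constant |
| Protocol 8.3 | Antidepressant regimen unchanged | Hold constant |
| Protocol 6.1 | Ramelteon is the only treatment described | No non-drug therapy planned |
| Protocol 8.4 | Non-drug insomnia treatment to be added or changed | Opposite |

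A real instruction to add therapy would need to say which therapy, for whom and when; nothing does. Similar slips occur nearby. The 8.3 sentence quoted as "Addition of antidepressant will not allowed after the time of 4 weeks prior to start of the run-in period" lacks a verb. Section 7.5 item 2 gives as a reason for withdrawal that continuing "would pose an acceptable risk to his/her health", where items 1 and 7 of the same list speak of unacceptable risk. The two protocol texts differ in 7.3 and 8.3 but not in 8.4, so whichever is later, revision did not touch the sentence. It is complete in both.

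**Does anything else govern the point?** Section 7.3 lists only drugs. Section 9.1.3 and SAP 6.2.1 concern history and baseline. Section 9.1.13 asks at each visit about psychotherapeutic drugs only. SAP 6.1.4.1.1 has a deviation category covering excluded therapy, but the protocol excludes no non-drug therapy. So 8.4 is the only rule.

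**How large would a co-intervention have to be?** The plan gives no figure to reproduce, because N = 30 is set by feasibility (Protocol 13.3). The inputs are n = 30 and a two-sided 5% level (Protocol 13.1.5). I assume that all 30 patients have data and that there is no drug effect and no natural change.

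The test rejects when |mean change| / SD exceeds t(0.975, 29)/√30 = 2.045/5.477 = 0.373. A uniform shift of about 0.37 SD in all 30 patients therefore reaches the threshold.

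If only k patients shift, each by e residual SDs, the split itself widens the observed SD:

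- expected mean = k·e/30
- expected variance = 1 + e²·k(30 − k)/(30·29)
- threshold: (k/30)²·e² = 0.1394·[1 + e²·k(30 − k)/870], where 0.1394 = 0.3734²

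| k | Left coefficient of e² | Right coefficient of e² | e needed |
|---|---|---|---|
| 30 | 1 | 0 | √0.1394 = 0.37 |
| 15 | 0.2500 | 0.1394 × 225/870 = 0.0361 | √(0.1394/0.2139) = 0.81 |
| 10 | 0.1111 | 0.1394 × 200/870 = 0.0321 | √(0.1394/0.0791) = 1.33 |
| 3 | 0.0100 | 0.1394 × 81/870 = 0.0130 | no solution |

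For k = 3, even with no residual noise, t = 0.1 × 5.477/√(81/870) = 0.5477/0.3051 = 1.80, which is below 2.045 whatever the value of e. Neither k nor e is in the documents, so these figures give scale only and do not estimate what happened.

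**The case against.** The strongest reply is that the evidence for a dropped 'not' is also evidence that investigators would supply it themselves. The literal instruction can hardly be carried out, since no therapy, provider or timing is given. The CRF is in Japanese (Protocol 12.1), so the English may be a translation, and what sites were told in Japanese is not in the file. The study is exploratory and openly uncontrolled, so natural change and regression to the mean already limit attribution. All of this stands, and it keeps the harm conditional. It does not make the sentence correct: it is an operative instruction with no contrary rule elsewhere.

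A reader might infer that sites were told to add therapy and that the result is therefore biased. The documents do not show that any site read 8.4 literally. A reader might also infer that a handful of literal readings could produce a significant result by themselves. The k = 3 calculation speaks against that under its stated assumptions.

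It can also be said that correcting one word does not make the rule checkable, and this is right. Protocol 14.2 records deviations that are noticed but prompts no one to ask. Section 7.4 item 6 has participants report treatment received at other hospitals, which is only a partial route.

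**Conclusion.** The sentence is wrong as written and should be corrected. That it states the opposite of the intended rule is an inference, though a well-supported one, so the sponsor needs to confirm it.

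The effect on the trial is unknown, and it is zero if every site understood 'should not'. The one figure that needs no assumption about partial uptake is the 0.37 SD uniform shift in all 30 patients; it still assumes complete data and no other source of change. With partial uptake the requirement rises to about 0.81 residual SDs for 15 patients and 1.33 for 10. Wide literal use could therefore influence the primary test, while isolated use is unlikely to decide it. The uncontrolled design already restricts what can be attributed to ramelteon, and 8.4 adds an avoidable further source of ambiguity.

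**What to change.** The sponsor should confirm the intent, against the Japanese text if there is one. It should then amend 8.4 to say that non-pharmacological insomnia treatment *should not* be added or changed during the study, using the revision route in Protocol 6.4. Breaches that come to light are then recorded under Protocol 14.2 and counted in the existing SAP 6.1.4.1.1 category for excluded medication or therapy. Sample size, significance level and primary analysis are unaffected.

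The correction itself costs one word and an amendment. To check the rule systematically, add one short question at Visits 3 and 4 on whether any non-drug insomnia treatment was started or changed. That is a small extra data item, needed because 9.1.13 asks only about drugs.

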9.0 STUDY PLAN

9.1 Study Procedures

The principal investigator or investigator will collect data according to the following procedures. In principle, the same principal investigator or investigator should perform the examinations, observations, and evaluations in the same participant. The study schedule is provided in Appendix A.

9.1.1 Informed consent

Informed consent procedures are described in Section 15.3.

Study procedures may be started only after informed consent is obtained from the participant.

Participants who provided informed consent will be assigned participant identification codes for de-identification. The assigned participant identification codes will be used throughout the study period without changes.

9.1.2 Demographic data, medical history and prior medication

Demographic data will be obtained in terms of date of birth, sex, and history of alcohol consumption, and history of smoking.

Medical history will be obtained in terms of any clinically relevant diseases or symptoms that had disappeared or resolved within 1 year before the informed consent. Ongoing symptoms or diseases should be regarded as concurrent conditions (see Section 9.1.11).

9.1.3 History of insomnia

Regarding current insomnia, the following data will be obtained:

- Date of onset
- Initial/Recurrence
- Any non-pharmacological therapy

9.1.4 History of Depression

Regarding the current depressive episode, the following data will be obtained:

- Date of onset
- Initial/Recurrence
- Any use of psychotherapy

9.1.5 Physical examination

Physical examination will be performed. Findings of physical examination after the start of the treatment period will be compared with those before the treatment period, and assessed for any abnormalities that can be clinically relevant.

9.1.6 Body weight, height and Body Mass Index (BMI)

Body weight and height will be measured. BMI will be calculated by the sponsor, using the following equation:

$$\text{Body Mass Index (BMI)} = \text{Body Weight (kg)} / (\text{Height (m)})^2$$

Height will be measured to the nearest whole number in centimeters. Body weight will be measured to the first decimal place in kilograms. The calculated BMI value will be expressed to the first decimal place.

9.1.7 Actigraphy

At the end of the informed consent, an actigraph will be lent to each participant. After full instructions on actigraphy are provided to the participants, actigraphy recording will be started. Patients meeting the inclusion criteria on the basis of the data in the run-in period will keep the actigraph, and be instructed to wear it until the end of the treatment period.

Participants will be instructed to bring the actigraph at each study visit. For analysis of the data recorded in the actigraph, the actigraph will be connected to a computer with an actigraphy data analysis software installed, and the following data will be transferred to the analysis software: sleep latency, total nocturnal sleep time, nocturnal wake time, the number of nocturnal awakenings, sleep efficiency and daytime activity level (step counts). For each of these parameters, the validity of the measured data will be checked according to the "Procedures for actigraphic sleep assessment" prepared separately, and the data during the run-in period (Weeks -1 to 0) and the treatment period (Weeks 3 to 4 and 7 to 8) will be recorded in the case report form. The actigraph device will be retrieved after completion of the actigraphy recording on the 3 occasions, or when the participant is withdrawn from the study.

9.1.8 Sleep diary

At the end of the informed consent, a sleep diary will be provided to each participant, with instruction on how to keep the diary during the study period. The following diary data during the run-in period (Weeks -1 to 0) and the treatment period (Weeks 3 to 4 and 7 to 8) will be recorded in the case report form: sleep latency, bedtime hour,

awakening hour and number of nocturnal awakenings. Any missing entries, discrepancies, or other potentially dubious entries in the sleep diary will be checked with the participant, and explained in the sleep diary by the participant. Accordingly, necessary additions and corrections will be made to the sleep diary, and recorded in the case report form.

9.1.9 17-item Hamilton Rating Scale for Depression (HAM-D17)

The Hamilton Rating Scale for Depression (HAM-D) is a questionnaire used to rate the severity of depression based on general symptoms of depression, including physical symptoms. The rater will assess individual items on a scale from 0 to 2, 3, or 4 depending on the items, based on an interview with the participant.⁶⁾ The time frame assessed by the HAM-D is one week before each visit. This study will use the 17-item version (HAM-D17), and the scores of individual items and the total score will be assessed and recorded in the case report form.

9.1.10 Patient Global Impression (PGI)

The Patient Global Impression (PGI) is a patient-rated scale to measure the degree of any improvement (or worsening). Participants will rate their own condition compared with the run-in period (before the start of study treatment), and enter the score in the PGI form. The principal investigator or investigator will record the score in the case report form.

9.1.11 3 Dimensional Sleep Scale (3DSS)

The 3 Dimensional Sleep Scale (3DSS) is a patient-administered questionnaire developed in Japan, and used to assess sleep dimensions including sleep phases.⁷⁾ At each visit, participants will assess their own condition within the past month and complete the 3DSS form. The principal investigator or investigator will record the results of 3DSS in the case report form.

9.1.12 Columbia Suicide Severity Rating Scale (C-SSRS)

The C-SSRS is a questionnaire developed by researchers at Columbia University as a tool to help systematically assess suicidal ideation and behavior in the individuals during participation in a clinical research.¹³⁾¹⁴⁾ The C-SSRS consists of 3 questions addressing suicidal behavior and 5 questions addressing suicidal ideation, with subquestions assessing the severity. The principal investigator or investigator will perform the C-SSRS assessment based on an interview with the participant. Since this is performed to detect any signs of suicide during the study period, the C-SSRS assessment results will not be recorded in the case report form.

9.1.13 Concomitant medications

Concomitant medications are any psychotherapeutic drugs (Drugs for Insomnia, Antidepressant) that are used in addition to the study drug, and include drugs prescribed by doctors or over-the-counter drugs purchased by the participants. At each visit, participants will be interviewed about any psychotherapeutic drugs used other than the study drug from the time of informed consent to the end of the study and specific usage (drug name).

